Hot snare polypectomy versus endoscopic mucosal resection for small colorectal polyps: a randomized controlled trial (HSP vs HSPSI)

NCT No. : NCT 02239536

Document date : August 30, 2019

Methods

The study is a prospective randomized-controlled trial and was performed at two academic hospitals (Seoul St. Mary's Hospital and Incheon St. Mary's Hospital) from June 2014 to December 2017. The study protocol was approved by the Institutional Review Board of the Catholic Medical Center (Assignment No. XC14TIMI0039K) and registered with clinicaltrials.gov (NCT 02761213). Informed consent was obtained from all patients before they were enrolled.

Study population

Patients who underwent a screening, surveillance, or diagnostic colonoscopy were prospectively enrolled in the study. The inclusion criteria were patients with over the age of 30 years who provided informed consent and who had at least one small colorectal polyp (5-10 mm) with neoplastic features on narrow band imaging (NICE classification II).

Patients were excluded if they have a bleeding tendency or ever taken antiplatelet or anticoagulation therapy within 1 week before undergoing the procedure, an inflammatory bowel disease such as Crohn's disease and ulcerative colitis, a polyposis syndrome, or an inability to provide informed consent. When detecting the ineligible polyps with NICE classification I/III or more than a size of 10 mm, they were treated as per usual clinical protocol.

Procedures

All patients were prepared with a 2-L polyethylene glycol plus ascorbic acid solution (Coolprep®, Taejoon Pharm., Seoul, Korea). All colonoscopy was performed by two highly experienced endoscopists ([name] and [name]) using a high-definition endoscope (CF-HQ290I, CF-H260AI, or PCF-Q260AZI; Olympus Co, Japan). The morphology of the polyp was described by Paris classification. The size of a detected polyp was measured using the opening width of the biopsy forceps. When an eligible polyp (a 5-10 mm polyp with NICE classification II) were detected, it was randomly allocated to either HSP or EMR group. An oval snare (SnareMaster®, Olympus Co, Japan or Optimos®, Taewoong Co, Korea) with Endocut or Forced Coagulation current of an electrosurgical unit (VIO300D; Erbe Elektromedizin GmbH, Tubingen, Germany) was used for polypectomy. When the polyp was assigned to EMR group, submucosal injection with normal saline was performed in advance of polypectomy. The resected specimen was retrieved using endoscope suction channel. Two biopsies were obtained

from the most probable residual tissue at the polypectomy site after irrigation, air inflation, and close observation with white-light and narrow-band imaging. Each patient was allowed for enrollment of a maximum of 2 sequential polyps from the cecum.

Immediate bleeding indicates continuous bleeding over 30 seconds requiring any form of endoscopic hemostasis (epinephrine injection, clipping or coagulation) immediately or within 24 hours after polypectomy whereas delayed bleeding was defined as bleeding from the post-polypectomy site between 24 hours and 2 weeks after polypectomy.

The resected specimens and biopsy specimens were reviewed by 3 highly-experienced gastrointestinal pathologists who were blinded to the clinical information and resection techniques for evaluation the involvement of adenomatous tissue at the resection margin. Complete resection was defined as absence of neoplastic tissue from the two additional biopsies of the polypectomy site whereas involvement of resection margin was defined as absence of neoplastic tissue at the margin of the resected specimen. When the involvement of resection margin could not be determined because of electrocautery effect or tangential tissue section, it was classified as “inconclusive.”

Study outcomes

The primary study outcome was a comparison of complete resection rates between two polypectomy techniques.

The secondary outcomes included involvement of resection margin and post-polypectomy adverse events including immediate/delayed bleeding and perforation between the two groups.

Sample size calculation and statistical analysis

There was no exact report of the incomplete resection rate of HSP and EMR for 5-10 mm neoplastic polyps at the time of the study design. We assumed the incomplete resection rate of HSP to be 15% and that of EMR was 5%. Estimated sample size was 310 polyps (155 per group) with a α -value of 0.05, power of 80%, and a 10% of dropout rate.

Chi-square test or the Fisher’s exact test was used to compare categorical variables. The unpaired 2-sample t test was used for continuous variables. Binary logistic regression was used for multivariate analysis. All data analyses were performed by using Statistical Package for the Social Science for Windows (version 24, IBM corp. SPSS Inc, Chicago, Ill, US).

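### The logistic regression makes no allowance for two polyps from one patient: a minor flaw that touches patient-level predictors, and the treatment tests only if second polyps were not allocated independently

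*Combined protocol and SAP*

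**What the plan says.** Under Procedures, each eligible polyp is randomised when it is found: "it was randomly allocated to either HSP or EMR group". A patient can contribute more than one: "Each patient was allowed for enrollment of a maximum of 2 sequential polyps from the cecum". The text does not say whether a second polyp was allocated independently of the first.

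Under Sample size calculation and statistical analysis, the target is 310 polyps, 155 per group. Categorical outcomes are compared by chi-square or Fisher's exact test, and "Binary logistic regression was used for multivariate analysis". No covariates are listed, and nothing there mentions more than one polyp per patient.

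The documents name some factors that could enter such a model. Three are shared by a patient's polyps: hospital ("was performed at two academic hospitals"), indication ("Patients who underwent a screening, surveillance, or diagnostic colonoscopy were prospectively enrolled in the study") and endoscopist ("All colonoscopy was performed by two highly experienced endoscopists"). Two can differ between polyps in one patient: size ("The size of a detected polyp was measured using the opening width of the biopsy forceps") and morphology ("The morphology of the polyp was described by Paris classification").

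**The concern.** Two polyps removed from one patient share an operator, a bowel preparation and a colon, so their outcomes may be positively correlated. A logistic regression that treats every polyp as a separate observation then overstates the information on any factor common to both. Its intervals are too narrow and its p-values too small.

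The treatment comparison is different, because treatment is assigned polyp by polyp. What happens there depends on how the two allocations within a patient relate to each other, which the plan leaves unsaid. At stake are statements about patient-level predictors of incomplete resection and, only if allocations were linked, the primary comparison.

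**Working it through.** **The plan's own figure.** Inputs from the sample size section: incomplete resection 15% v 5%, alpha 0.05 (taken as two-sided), power 80%, dropout 10%.

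n per group = [1.96·√(2·0.10·0.90) + 0.8416·√(0.1275 + 0.0475)]² / 0.10² = (0.8315 + 0.3521)² / 0.01 = 140.1, so 141. Dividing by 0.9 gives 157 per group (314 in total); multiplying by 1.1 gives 156 (312). The stated 310 is reproduced to within about 1%. With about 140 evaluable polyps per group, expected events are 0.15·140 + 0.05·140 = 28.

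**Assumed inputs.** The documents give neither f, the share of polyps from two-polyp patients, nor rho, the within-patient correlation of the outcome. I use f = 0.2, 0.5 and 0.8. The share of patients with two polyps is (f/2)/(1 − f/2), that is 11%, 33% and 67%. I use rho from 0.05 to 0.3.

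**Treatment, allocations independent.** Same-arm and opposite-arm pairs are then equally likely. With v1 = 0.15·0.85 = 0.1275 and v2 = 0.05·0.95 = 0.0475, the design effect is

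1 + (f·rho/2)·[1 − 2√(v1·v2)/(v1 + v2)] = 1 + 0.0553·f·rho.

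Under the null v1 = v2, the bracket is zero and the design effect is exactly 1. At 15% v 5%, with every polyp paired and rho = 0.2, it is 1.011, and 310 becomes 313. Simulated chi-square size with every polyp paired was 4.9–5.3% for rho from 0 to 0.9.

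**Treatment, allocations linked.** Same-arm pairs give 1 + f·rho. Opposite-arm pairs give 1 − f·rho under the null and 1 − 0.889·f·rho at 15% v 5%. With every polyp paired and rho = 0.2, these imply 372 polyps (310 × 1.20) and 255 (310 × 0.822). Simulated size at (f, rho) = (0.8, 0.3):

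| Test | independent | same arm | opposite arm |
|---|---|---|---|
| Chi-square | 5.0% | 7.8% | 2.5% |
| Treatment term, naive logistic | 4.6% | 7.4% | 2.2% |
| Treatment term, clustered | 5.0% | 5.1% | 4.7% |

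**Patient-level predictor.** The design effect is 1 + f·rho. True size is 2·[1 − Φ(1.96/√DE)], and the interval should be wider by √DE − 1. The simulation columns use 280 polyps, about 28 events, a three-term model and a 50/50 patient-level factor (40,000 replicates); clustered means the uncorrected sandwich.

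| f, rho | DE | size by formula | widening | simulated naive | simulated clustered |
|---|---|---|---|---|---|
| 0.2, 0.05 | 1.01 | 5.1% | 0.5% | 4.7% | 4.7% |
| 0.5, 0.1 | 1.05 | 5.6% | 2.5% | 5.2% | 4.8% |
| 0.5, 0.2 | 1.10 | 6.2% | 4.9% | 5.7% | 4.9% |
| 0.8, 0.3 | 1.24 | 7.8% | 11.4% | 7.2% | 4.9% |

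**Polyp-level predictor.** The design effect is 1 + f·rho·r, where r is the factor's own within-patient correlation. At r = 0.3, size is 5.2% at (0.5, 0.1) and 5.8% at (0.8, 0.3). At r = 0 there is no distortion.

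**Does clustering restore 5% for other kinds of patient-level factor?** Same design, independent allocation, naive v uncorrected clustered size (Monte Carlo error about 0.2–0.3 points), in the order of the rows above:

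- Continuous factor: 5.0 v 5.9%, 5.6 v 6.2%, 5.9 v 6.2%, 7.9 v 6.7%. In a further set of runs the uncorrected sandwich gave 5.8–6.6%, and the Mancl-DeRouen correction 5.2–5.6%.
- 20/80 binary factor: 3.3 v 3.4%, 3.9 v 3.5%, 4.1 v 3.7%, 5.6 v 3.9%.

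**The case against.** The strongest reply is that the standard remedy is less clean than it looks. With about 28 events, the plain sandwich error left a continuous patient-level term at roughly 6–7%. It did slightly worse than the naive error in the two mildest scenarios and clearly helped only at the extreme. For a 20/80 factor the naive test was already conservative below the extreme. This stands, and it is why the fix calls for a small-sample correction.

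Second, the plan lists no covariates, so the affected terms may not exist. This also stands and makes the point conditional. Likewise, the absence of clustering is inferred from a one-paragraph analysis section that is silent on it; it is not a declared choice.

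Third, the distortion is trivial unless f and rho are both large, and the documents support no particular value of either. That is fair, and it caps the severity.

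A reader might go the other way and infer that the sample size should have been inflated by 1 + rho, or that the primary test is anti-conservative. The documents do not support this. That inflation applies when both of a patient's polyps receive the same treatment, whereas the Procedures section describes allocation of each polyp as it is detected.

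**Conclusion.** The omission is real but minor. If second polyps were allocated independently, the chi-square/Fisher comparison, the treatment term and N = 310 need no change. Patient-level predictors, if modelled, then generally have standard errors that are too small: about 5–6% size for f = 0.2–0.5 and rho = 0.05–0.2, up to about 7–8% at f = 0.8 and rho = 0.3, and no inflation for a 20/80 factor below that extreme. Polyp-level factors are affected less, or not at all.

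If allocations were linked, the treatment tests are mis-sized too, in the direction set by the pairing. Nothing in the documents shows that they were linked, so that case is a question for the authors and not a finding.

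The conclusion rests on positive within-patient correlation and on assumed f and rho.

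**What to change.** 1. State whether a patient's second polyp was allocated independently of the first, and report the numbers of one-polyp, same-arm and split-arm patients so that this can be checked.
2. Fit the planned logistic model with standard errors clustered on patient, an independence working correlation and a small-sample bias correction (for example Mancl-DeRouen). The odds ratios stay as planned; only standard errors, intervals and p-values move.
3. Keep chi-square/Fisher as the primary test on condition that allocations were independent. If they were linked, use the patient-clustered treatment estimate for the primary comparison.

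The cost is one re-run of the model and one small table, with no new patients or data. Intervals for patient-level terms widen by about 0.5–11% over the assumed ranges, and a little more with the correction. The model's treatment Wald test loses up to about 2 points of simulated power before the correction (80.3 to 80.2% at f = 0.2, rho = 0.05; 80.0 to 78.1% at f = 0.8, rho = 0.3) and a little more with it. Tests of unbalanced binary factors will be slightly conservative.

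### Does the plan need a rule for tracing a delayed bleed to one of two sites when a patient has a polyp in each arm?

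*Combined protocol and SAP*

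**What the plan says.** Under Procedures in the combined protocol and SAP, each eligible polyp is randomised on its own: "it was randomly allocated to either HSP or EMR group". The same section caps the number per patient: "Each patient was allowed for enrollment of a maximum of 2 sequential polyps from the cecum". Nothing requires a patient's two polyps to share an arm.

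The two bleeding outcomes are defined together. For the first, "Immediate bleeding indicates continuous bleeding over 30 seconds requiring any form of endoscopic hemostasis", at once or within 24 hours. For the second, "delayed bleeding was defined as bleeding from the post-polypectomy site between 24 hours and 2 weeks after polypectomy". The second definition has a place and a time window but no endoscopic criterion.

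Study outcomes lists, among the secondary outcomes, "post-polypectomy adverse events including immediate/delayed bleeding and perforation between the two groups". For the test, Sample size calculation and statistical analysis says only "Chi-square test or the Fisher’s exact test was used to compare categorical variables".

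Under Study population, ineligible polyps are dealt with outside the trial. The text does not say whether, or when, they were removed.

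**The concern.** Immediate bleeding needs endoscopic hemostasis, so someone looks at the site and the arm is known. A delayed bleed occurs after the patient has left, and it may settle without a second endoscopy. If that patient has one site in each arm, the arm is known only if the source was seen. The plan describes no follow-up contact, no repeat endoscopy, nobody who judges the source, and no handling of a bleed that cannot be traced. Pathologists are stated to be blinded, but nothing comparable is said about bleeding.

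This is separate from the usual worry about two correlated polyps in one patient. Correlation affects the standard error, whereas this affects which column an event goes into, and a clustered model would not repair it. If untraced events were assigned at random, the difference between arms would shrink and the techniques would look more alike on a safety outcome than they are. At stake are the per-arm counts of delayed bleeding and the difference between them.

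**Working it through.** **The plan's own figure.** There is none for delayed bleeding. The only size given is 310 polyps, 155 per arm, for the primary outcome. It reproduces with 15% vs 5%, two-sided alpha 0.05 and 80% power.
- Unpooled: (1.960 + 0.842)² × (0.15×0.85 + 0.05×0.95) / 0.10² = 7.85 × 0.175 / 0.01 = 137.4, so 138. Then 138/0.9 gives 154 per arm, 308 in total.
- Pooled: 141 per arm. Then 141/0.9 gives 157 per arm, 314 in total.

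The stated 310 lies between the two, so 155 per arm is used below.

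**Inputs that the documents do not give (assumed).** The share f of polyps that come from two-polyp patients is set at 25%, 50% or 80%. A patient's two polyps are allocated independently 1:1. The delayed-bleeding rate is 0.5% to 2% per polyp.

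**How many polyps sit in split-arm patients.** Pairs = 310f/2. Patients = 310 − pairs. Half of the pairs are split, and each holds two polyps, so split polyps = 310f/2.

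| f | Patients | Split-arm patients | Split polyps (share of 310) |
|---|---|---|---|
| 25% | 271 | 19 (7%) | 38.75 (12.5%) |
| 50% | 233 | 39 (17%) | 77.5 (25%) |
| 80% | 186 | 62 (33%) | 124 (40%) |

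Independent allocation matters here. If the second polyp always went to the other arm, split polyps would double. If it always went to the same arm, there would be none.

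**Expected delayed bleeds in those patients** = split polyps × rate.
- At 0.5%: 0.2 / 0.4 / 0.6.
- At 1%: 0.4 / 0.8 / 1.2.
- At 2%: 0.8 / 1.6 / 2.5.

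The whole trial would expect 310 × 0.005 = 1.6 to 310 × 0.02 = 6.2 events.

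**Chance of at least one at 1%.**
- Any delayed bleed in a split-arm patient: 1 − 0.99^(split polyps) = 32% / 54% / 71%. This counts bleeds whose source was seen, which raise no problem.
- A bleed with an unseen source, if half of the sources were unseen (assumed): 1 − 0.995^(split polyps) = 18% / 32% / 46%.
- If all sources were seen: zero.

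**Effect of one ambiguous event on the difference.**
- Left unassigned: 1/155 = 0.65 points.
- Credited to the wrong arm: 2/155 = 1.29 points.

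**Effect of random assignment.** If every bleed in a split-arm patient were assigned by chance, the true difference would be multiplied by 1 − split share = 0.875 / 0.75 / 0.60. If only half had unseen sources, the factor would be 1 − (split share)/2 = 0.94 / 0.875 / 0.80.

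**Effect on the test.** Fisher's exact test, two-sided, with 155 per arm: 5 vs 0 gives p = 0.061 and 6 vs 0 gives p = 0.030. Significance therefore needs at least six events, all in one arm. Even at 2%, the expected total across both arms is only about six.

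**What the definition does with an untraced bleed.** The definition counts bleeding only when it comes from a polypectomy site. Read literally, a bleed that nobody traced to a site does not qualify, so the count is site-specific as written. A looser reading, in which untraced bleeds were counted and assigned somehow, is possible, but no sentence supports it over the literal one.

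**The case for a change.** The strongest reply is that naming a site demands a conclusion without saying how it is reached. With two study sites, the definite article in the definition does not pick one. If the phrase is taken to require a seen source, bleeds that settled without endoscopy go uncounted, and the plan does not say that either. Rare safety outcomes are also read from raw counts rather than p-values, and one event credited to the wrong arm is worth 1.3 points, the same order as the assumed rates.

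Much of this stands. The method of confirmation really is absent, and so is a rule for untraced bleeds. Three things limit it:
- The 1.3-point figure needs a wrong assignment, which no passage shows. Leaving the event out costs half as much. The rates it is set against are assumptions, not the plan's figures.
- A strict rule, such as counting a bleed in any patient with several resection sites only when the source was seen, would do harm. It would discard events in patients whose study polyps were both in one arm, where the arm is known if nothing else was resected.
- A separate analysis restricted to patients with all study polyps in one arm would keep 87.5% / 75% / 60% of polyps, or about 2.7 / 2.3 / 1.9 expected events at 1%. That is too few to inform anyone.

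Non-study polyps might add possible sources, but the documents do not say that they were resected, so nothing can be built on them.

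**Conclusion.** The observation is accurate, but it is a missing detail that analysts fill sensibly: they use the site where the record shows it and say so where it does not. The definition as written yields a site-specific count, and no result is shown to be wrong.

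The reach is one component of one secondary outcome. At an assumed 1% rate, 0.4 to 1.2 events are expected in split-arm patients, or 0.2 to 0.6 if half of the sources were unseen. Each is worth 0.65 to 1.3 points on the difference, and one or two such events would rarely change the test. Scarcity of events limits this comparison far more than attribution does.

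A change to the plan would also gain little now. The study ran to December 2017 and the document is dated August 2019, so site confirmation cannot be added afterwards. What remains is a matter for the text of the results.

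This rests on assumed values for the share of two-polyp patients, independent allocation of the second polyp, the bleeding rate and the fraction of unseen sources. None of these is in the documents. The view would change only if a claimed difference in delayed bleeding turned on a few untraced events in split-arm patients.

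### Does the missing severity threshold for delayed bleeding undermine the bleeding comparisons?

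*Combined protocol and SAP*

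**What the plan says.** The Procedures section gives the two definitions in one sentence. The first is demanding: "Immediate bleeding indicates continuous bleeding over 30 seconds requiring any form of endoscopic hemostasis", with the hemostasis given "immediately or within 24 hours after polypectomy". The second is not: "delayed bleeding was defined as bleeding from the post-polypectomy site between 24 hours and 2 weeks after polypectomy". It names a site and a time window and no other criterion.

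Under Study outcomes, the secondary outcomes include "post-polypectomy adverse events including immediate/delayed bleeding and perforation between the two groups". The statistical section adds only that a chi-square or Fisher's exact "test was used to compare categorical variables". It sizes the trial on incomplete resection (15% for HSP, 5% for EMR), giving 155 polyps per group. It states no bleeding rate and no power for bleeding.

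**The concern.** A bleed in the first 24 hours that stops by itself counts in neither outcome, whereas any bleed from the site after 24 hours counts as delayed. The document does not say whether an unwritten threshold was used when delayed events were classified.

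Two things could be at stake. A reader who sets the two rates side by side might conclude that delayed bleeding is relatively common when the definition alone produced the contrast. A reader who adds them might take the sum for all bleeding to 2 weeks, although untreated first-day bleeds are left out. In addition, a delayed bleed as reported could be a trivial event or one that needed a repeat procedure.

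**Working it through.** **1. The plan's own figure.** The only quantity stated is the sample size, and bleeding does not enter it. Inputs from the statistical section: 15% and 5%, alpha 0.05 (taken as two-sided), power 80%, dropout 10%.

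- n = [1.96·√(2·0.10·0.90) + 0.8416·√(0.15·0.85 + 0.05·0.95)]² / 0.10² = (0.8316 + 0.3521)² / 0.01 = 140.1, so 141 per group.
- With dropout: 141/0.9 = 156.7, so 157; or 141 × 1.1 = 155.1, so 156. The plan states 155, which is close enough to count as reproduced.

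No wording of the bleeding definitions would move this number.

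**2. The definitions side by side.**

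| | Immediate | Delayed |
|---|---|---|
| Window | 0 to 24 h | 24 h to 2 weeks |
| Duration | over 30 s, continuous | not stated |
| Treatment | endoscopic hemostasis | not stated |
| Applies to | both arms | both arms |
| Planned contrast | HSP vs EMR | HSP vs EMR |

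The asymmetry runs between columns. The planned contrast runs within a column.

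**3. Effect on the planned contrast.** Let p_H and p_E be the risks of any bleed in one window, and h the share needing hemostasis. With a threshold the risk ratio is h·p_H / (h·p_E) = p_H / p_E, a factor of h/h = 1. If h differed by arm, the thresholded outcome would still be a fair comparison of treated bleeding, because the rule is the same for both arms.

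**4. Effect on a contrast nobody planned.** All inputs here are assumed: h as above, and w, the share of bleeds falling in the first 24 hours.

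- With equal numbers of bleeds in each window and no delayed threshold, delayed bleeding looks 1/h times as frequent: 1/0.8 = 1.25, 1/0.5 = 2, 1/0.2 = 5. If both windows in fact carried the same threshold, the ratio is 1.
- The sum of the two outcomes captures 1 − w(1 − h) of all bleeds. At w = 0.5 this is 0.90, 0.75 and 0.60 for h = 0.8, 0.5 and 0.2. The shortfall w(1 − h) involves only first-day bleeds. It vanishes if all of those needed hemostasis, whatever happened later, and also if w = 0.

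These results restate h and w. They say nothing about what happened in this trial.

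**5. How much information is at issue.** At an assumed delayed-bleed rate of 1% per polyp, 310 polyps yield 310 × 0.01 = 3.1 events, or 0.6 to 2.5 if only treated bleeds count (h from 0.2 to 0.8). The 310 already includes the dropout allowance, so the evaluable count would be lower.

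For power with 155 per arm and two-sided alpha 0.05: Φ{[|p1 − p2|·√155 − 1.96·√(2·p̄·q̄)] / √(p1·q1 + p2·q2)}, where p̄ is the mean of p1 and p2, and q = 1 − p. For 1% against 3% this is Φ[(0.2490 − 0.3881)/0.1975] = Φ(−0.704) = 24%. For 2% against 5% it is 30%, and for 0.5% against 2% it is 22%. At rates of this order the bleeding comparisons are close to descriptive under either definition.

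**The case for a change.** The strongest case for acting is that clarification is cheap and would make a safety result easier to read. The slash in the phrase naming immediate and delayed bleeding does not rule out a combined count. With only a few events expected, the classification of one or two changes the reported rate. Each patient may also contribute two polyps. A delayed bleed seen at endoscopy is easier to assign to one site than one known only from the patient's account, so a split by treatment would carry some information about attribution.

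Part of this stands. The delayed definition is silent on severity, and a reader would want to know how many delayed bleeds were treated. The rest does not support a change:

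- A slash between two separately defined events is weak evidence of a planned total, and no total is defined.
- The definitions need not match. Continuous bleeding for 30 seconds is something an endoscopist observes, and the document describes no such observation after the first day.
- The proposed split depends on hemostasis having been recorded for delayed bleeds, which the document does not say. A combined 2-week outcome built from it would be new and post hoc, and might lack the 30-second element.
- Stating that untreated first-day bleeds were not counted as immediate bleeding repeats what the definition already conveys.
- The difficulty of assigning a bleed to one of two sites is separate from the missing threshold, and nothing in the document shows that it favors one arm.

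**Conclusion.** The observation is correct, but the plan needs no change. The two bleeding definitions differ in strictness, each is applied alike to HSP and EMR, and the plan compares arms within each definition. The between-arm risk ratio is unaffected when the share of treated bleeds is equal in the arms, and no between-arm bias has been shown. The primary outcome and the 310-polyp sample size are untouched.

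The cross-window distortions (1.25 to 5 times; 60% to 90% captured at w = 0.5) rest wholly on assumed values of h and w and apply to an analysis that is not planned. Their direction also depends on there having been no unwritten threshold for delayed bleeding, which the document leaves open.

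What is left is a gap in description that analysts fill sensibly when they report. They present the two bleeding types separately, as they are defined, and say how delayed events were classified and, where recorded, how many were treated. This conclusion assumes that follow-up for delayed bleeding was the same in both arms. The document does not describe that follow-up, but gives no reason to think it differed.

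### Does the plan need a histology-based primary denominator because polyps are randomised on optical appearance?

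*Combined protocol and SAP*

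**What the plan says.** Study population admits patients on optical criteria: "at least one small colorectal polyp (5-10 mm) with neoplastic features on narrow band imaging (NICE classification II". Polyps classed as NICE I or III are ineligible and are treated outside the trial. Procedures sets the point of allocation: "When an eligible polyp (a 5-10 mm polyp with NICE classification II) were detected, it was randomly allocated to either HSP or EMR group". Histology comes later, from pathologists who do not know the technique used.

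Procedures also defines the endpoint: "Complete resection was defined as absence of neoplastic tissue from the two additional biopsies of the polypectomy site". It sets no condition that the resected polyp itself be neoplastic. Study outcomes adds only this: "The primary study outcome was a comparison of complete resection rates between two polypectomy techniques". No denominator or analysis set is given there or in the statistics section.

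Sample size calculation and statistical analysis introduces the planning figures with: "There was no exact report of the incomplete resection rate of HSP and EMR for 5-10 mm neoplastic polyps". It then assumes incomplete resection of 15% for HSP and 5% for EMR, and arrives at 310 polyps (155 per group) with "power of 80%, and a 10% of dropout rate". It does not say what counts as dropout.

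**The concern.** Optical diagnosis is imperfect, so some randomised polyps may turn out not to be neoplastic. Such a polyp leaves no neoplasia behind, and its site biopsies will be clear even if tissue remains. Under the written definition it is a success for either technique.

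The planning rates follow a sentence about neoplastic polyps. If the analysis counts every randomised polyp, the reported rates would look better than those for neoplastic polyps, and the absolute difference would be smaller than the one apparently planned for. A reader could not tell from the plan which population the headline rates describe, and the choice could be made after the results were known.

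**Working it through.** **Inputs.** Incomplete resection p₁ = 0.15 (HSP) and p₂ = 0.05 (EMR), alpha 0.05, power 80%, 10% dropout and 155 per group all come from the sample size section. Sidedness is not stated; two-sided is assumed because it reproduces the stated size. The non-neoplastic share q is **not in the documents**; 2% to 20% is an assumed range.

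**The plan's own figure.** For two proportions with pooled variance and p̄ = 0.10:

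n = [1.96·√(2·0.10·0.90) + 0.8416·√(0.15·0.85 + 0.05·0.95)]² / 0.10² = (0.8316 + 0.3521)² / 0.01 ≈ 140.1 per arm.

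Dividing by 0.9 gives 155.7, in line with the stated 155. Rounding up to 141 first gives 157. The sample size is sound.

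**Effect of counting all randomised polyps.** Allocation precedes histology, so q is the same in both arms in expectation. The incomplete rate becomes p(1 − q), and the difference becomes (0.15 − 0.05)(1 − q) = 0.10(1 − q). The ratio 0.05(1 − q) / 0.15(1 − q) stays at 0.33.

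Power is shown at 140 per arm (155 × 0.9 = 139.5, rounded up). The last column restricts to neoplastic polyps, with 140(1 − q) per arm and 15% v 5%.

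| q | Complete, HSP v EMR | Difference (points) | Power, all randomised | Power, neoplastic only |
|---|---|---|---|---|
| 0 | 85.0% v 95.0% | 10.0 | 80.0% | 80.0% |
| 2% | 85.3% v 95.1% | 9.8 | 79.1% | 79.2% |
| 5% | 85.75% v 95.25% | 9.5 | 77.7% | 77.9% |
| 10% | 86.5% v 95.5% | 9.0 | 75.2% | 75.7% |
| 20% | 88.0% v 96.0% | 8.0 | 69.6% | 70.6% |

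A non-neoplastic share does cost power, but nearly the same amount on either denominator: restriction restores the difference and loses polyps. At q = 20% the choice is worth 70.6 − 69.6 = 1.0 point. If all 155 per arm are evaluable, the figures at q = 10% are 79.4% and 79.8%.

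**Scale of the shift.** At 15% v 5% with 140 per arm, the 95% half-width of the difference is 1.96·√[(0.1275 + 0.0475)/140] = 1.96 × 0.0354 = 6.9 points. The shift is 0.2 points at q = 2%, 1.0 at q = 10% and 2.0 at q = 20%, or about 3%, 14% and 29% of that half-width.

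**What a histology-based set would do.** A natural rule drops polyps whose specimen is read as non-neoplastic and whose site biopsies are clear, and keeps those with neoplastic site biopsies as failures. Exclusion then depends partly on the outcome. As an illustration with assumed figures, suppose 3% of completely resected HSP polyps are misread as non-neoplastic and none are in the EMR arm. Per 100 HSP polyps, 0.03 × 85 = 2.55 successes are removed, and incomplete resection becomes 15/97.45 = 15.4%. The difference is then 10.4 points, against 10.0 with all polyps kept. That 0.4-point error is close to the 0.5-point dilution at q = 5%, but it works against one arm. Equal dilution does not.

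**The case for a change.** The best case for a change is that the headline result is an absolute rate for each technique, and absolute rates are what dilution alters. The specimens are already read blind, so defining the set would need only a sentence and a table row. The planning rates are most naturally read as rates for neoplastic polyps. An unwritten denominator also leaves a choice open once outcomes are known.

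Most of this is true, and the omission is real. Three things limit its weight.

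- The sentence that assumes 15% and 5% names no population. The rates may equally describe polyps with neoplastic features on imaging, in which case nothing is diluted relative to planning.
- The rates are overstated only if the target is histologically neoplastic polyps, which the plan does not require. The endoscopist chooses a technique on optical appearance, so the all-randomised rate answers a relevant question and keeps the randomised comparison intact.
- The document is dated August 2019 and says the study ran to December 2017. A denominator written in now would not be prespecified.

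**Conclusion.** No change to the plan is called for. The plan omits the denominator, and the (1 − q) factor is exact when q is equal in the arms, as randomisation makes it in expectation. A chance imbalance would alter it: q of 10% in HSP and 5% in EMR gives 0.15 × 0.90 − 0.05 × 0.95 = 8.75 points.

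The consequence is small. The shift is 0.2 to 2.0 points over an assumed q of 2% to 20%. The upper end has no support in the documents, and the exclusion of NICE I polyps works against it. The rate ratio is unchanged, neither arm is favoured in expectation, the sample size reproduces, and the choice of denominator moves power by about 1 point at most.

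Both denominators are defensible. Writing in the histology-based set as primary would replace a set that preserves randomisation with a post-randomisation exclusion that removes only successes. Reasonable statisticians would differ on that trade. The ordinary way to fill the gap is in the report: state which polyps were counted, give the non-neoplastic number by arm, and show the other denominator alongside.
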